8.3. Sensitivity Analyses

Summaries of TWSTRS total score, CGIC, and PGIC will be provided at each visit and will identify assessments done in-clinic and assessments done remotely for the safety population. Summaries of TWSTRS total score, CGIC, and PGIC will be done for the Non-COVID-19 Impacted Analysis set.

This document is confidential.

9. Safety

The safety population will be used for all safety analyses. Safety will be assessed on the basis of AEs, clinical laboratory values (hematology, coagulation, chemistry, and urinalysis), pregnancy test results, vital signs, [REDACTED], spirometry, 12-lead ECG results, C-SSRS and the DSS.

9.1. Injection Site Evaluation

The number and percentage of subjects with an injection site reaction will be summarized by cycle and dose, along with the type of reaction. All injection site evaluation information will be provided in a listing.

9.2. Muscle Injection Record

The number and percentage of subjects who received study drug injection into each muscle will be summarized by treatment cycle and dose. All muscle injection record data will be listed.

9.3. Adverse Events

AEs will be coded using MedDRA version 22.0 or later. An AE will be considered treatment emergent if the event begins on or after the date of first dose of study medication or if the event begins before and worsens in severity after the date of first dose of study medication. An adverse event with a relationship to study medication of definite, probable, or possible is also considered to be treatment-emergent.

AEs will be summarized by system organ class (SOC) and preferred term (PT). An AE is considered related to study treatment if the relationship is considered as definite, probable, or possible. If the relationship to study treatment is missing, the AE will be counted as definite in summary tables. If the severity is missing, then the AE will be counted as severe in summary tables. Actual missing values will be presented in the listings.

Summary tables will be provided for treatment-emergent AEs (TEAEs) by dose and treatment cycle and overall for the following:

- Overall summary of TEAEs
- TEAEs by SOC and PT
- TEAEs by PT with a frequency of at least 3% overall
- TEAEs by SOC, PT, and maximum severity
- TEAEs by SOC, PT, and strongest study medication relationship
- Treatment-related TEAEs by SOC and PT
- Serious TEAEs by SOC and PT
- TEAEs resulting in study medication discontinuation by SOC and PT
- TEAEs of special interest by SOC and PT

[REDACTED]

In addition, summaries will be provided by the following dose groups:

- HDHF: High dose, high frequency group, defined as subjects who received a high dose (250 U or 300 U) for 3 or 4 cycles

This document is confidential.

- HDLF: High dose, low frequency group, defined as subjects who received a high dose (250 U or 300 U) for 1 or 2 cycles
- LDHF: Low dose, high frequency group, defined as subjects who received a low dose (125 U or 200U) for 3 or 4 cycles
- LDLF: Low dose, low frequency group, defined as subjects who received a low dose (125 U or 200 U) for 1 or 2 cycles

Subjects will appear in only one group, and TEAEs will be summarized for subjects in each group. Subjects who received a high dose for 2 cycles and a low dose for 2 cycles will be included in the HF group. Subjects who received a high dose for 1 cycle and a low dose for 1 cycle will be included in the HL group.

The overall summary of TEAEs will include the number and percentage of subjects with a TEAE, with treatment-related TEAEs, with serious TEAEs, treatment-related serious TEAEs, with TEAEs of special interest, [REDACTED], related to anaphylactic reaction, with toxin-related TEAEs, with TEAEs leading to death, and with TEAEs leading to study discontinuation. The number of events will also be provided. For TEAE summaries, the number and percentage of subjects will be presented by SOC and PT by treatment. Subjects will be counted only once for each SOC and for each PT within each SOC. For summaries by maximum severity and strongest relationship, if a subject has the same event more than once, the subject will be included only once at the worst severity or strongest relationship. Summary tables by SOC and PT will be sorted in descending frequency by SOC and then by PT within each SOC by the overall column. All AEs will be included in the listings. Listings will be provided for all AEs, serious AEs, and AEs resulting in study medication discontinuation. All information pertaining to AEs noted during the trial will be listed by subject, detailing the verbatim description given by the Investigator, preferred term, system organ class, start date, stop date, severity, action taken regarding study drug, outcome, and drug relatedness. The event onset will also be shown relative (in number of days) to the date of first dose of study treatment administration. In addition, a list of subjects who prematurely discontinue from the trial due to adverse events will also be provided.

[REDACTED]

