8.3 ADVERSE EVENTS AND SERIOUS ADVERSE EVENTS

8.3.1 DEFINITION OF ADVERSE EVENTS (AE)

For this protocol, an **AE** is any untoward medical occurrence (e.g., sign, symptom, disease, syndrome, intercurrent illness, clinically significant abnormal laboratory finding, injury, or accident) that emerges or worsens following administration of the study drug and until the end of study participation. The untoward medical occurrence may not necessarily have a causal relationship to the administration of the investigational product. An AE can therefore be any unfavorable and/or unintended sign (including a clinically significant abnormal laboratory result), symptom, or disease temporally associated with the use of a medicinal (investigational) product, whether or not related to the medicinal (investigational) product. A TEAE is one that occurs after any exposure to treatment.

A pre-existing condition is one that is present prior to the start of the study and is to be reported as part of the subject's medical history. It should be reported as an AE only if the frequency, intensity, or the character of the condition worsens during the study.

Any clinically significant change in the study safety evaluations, (e.g., vital signs, physical/neurological examinations, etc.) post-injection must be reported as an AE.

For each laboratory test result outside the reference range, the investigator must ascertain if the abnormal lab result is a clinically significant result for that individual subject. This determination, however, does not necessarily need to be made the first time an abnormal value is observed; the investigator may repeat the laboratory test or request additional tests to verify the results of the original laboratory test. If a laboratory value is determined to be a clinically significant result for a subject, this may be considered an AE.

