8.3.3.2 RELATIONSHIP TO STUDY INTERVENTION

Relationship of an AE to investigational product will be assessed as follows:

- **Definite:** There is a clinically plausible time sequence between the onset of the AE and the administration of investigational product; when the event responds to withdrawal of investigational product and recurs with re-administration of investigational product
- **Probable:** There is a clinically plausible time sequence between the onset of the AE and the administration of investigational product; the AE is unlikely to be caused by the concurrent/underlying illness, other drugs or procedures
- **Possible:** There may or may not be a clinically plausible time sequence between the onset of the AE and the administration of investigational product and a cause cannot be ruled out
- **Unrelated:** There is not a temporal or causal relationship to investigational product administration

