4.1. Primary Endpoints

The primary endpoints of this study are:

- The dose- and cycle-specific incidence of drug-related adverse events (AEs)
- The dose- and cycle-specific incidence of study drug discontinuation due to drug-related AEs
- The dose- and cycle-specific incidence of treatment-emergent immunogenicity

This document is confidential.

5. Analysis Sets

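### The SAP makes any related AE treatment-emergent with no onset condition, so a related AE that began before the first open-label dose can be counted in the tables serving the primary endpoint

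*SAP*

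**What the plan says.** SAP 9.3 gives two rules for treatment-emergence.

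- Onset rule: "An AE will be considered treatment emergent if the event begins on or after the date of first dose of study medication", or if it began earlier and became more severe after that date.
- Relatedness rule: "An adverse event with a relationship to study medication of definite, probable, or possible is also considered to be treatment-emergent". No onset date is mentioned.

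The same section handles blank causality: "If the relationship to study treatment is missing, the AE will be counted as definite in summary tables". It then tabulates treatment-related treatment-emergent AEs by dose and treatment cycle. Those tables serve the first primary endpoint in SAP 4.1, the incidence of drug-related AEs by dose and cycle.

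Protocol 8.3.1 defines an AE as an occurrence "that emerges or worsens following administration of the study drug and until the end of study participation". On treatment-emergence it says only: "A TEAE is one that occurs after any exposure to treatment". Relatedness plays no part in either definition. In Protocol 8.3.3.2 the weakest related category, *possible*, is worded: "There may or may not be a clinically plausible time sequence between the onset of the AE and the administration", with the added condition that a cause cannot be excluded.

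**The concern.** The two SAP rules do different jobs. The first ties an event to a point in time. The second ignores time and relies on the investigator's causality rating. In a trial whose primary safety endpoint is indexed by dose and cycle, an event that began before any OLS injection has no dose or cycle to belong to, and should not be in the numerator.

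The population makes this more than theoretical. Many subjects roll over from Study 1720302, which SAP 3.4 describes as a placebo-controlled trial of a single treatment with the same product. Some will therefore have had active drug before entering. Under inclusion criterion 3d (Protocol 5.1), subjects who reached Week 36 without meeting their target score can be followed in the OLS before being retreated. Protocol 9.6 carries the 1720302 injection date into their duration-of-effect calculation, so the earlier injection is not wholly outside the OLS analysis. An investigator could rate a new event in that untreated interval as possibly related to the drug.

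**Working it through.** The plan states no AE rate, power or precision for this endpoint, so there is no figure to reproduce. The check is mainly a reading of the rules, followed by simple arithmetic on size.

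**Step 1: what the relatedness rule adds.** Take a related AE with a known start date.

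- It begins on or after the first OLS dose: already treatment-emergent under the onset rule.
- It begins earlier and worsens after that dose: already treatment-emergent under the onset rule.
- It begins earlier and does not worsen: treatment-emergent only through the relatedness rule.

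The sentence is therefore either redundant or it admits the third kind of event.

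**Step 2: comparison with the protocol.** Under Protocol 8.3.1 an event of the third kind is not an AE at all if study drug means OLS drug. The SAP sentence has no counterpart there. The legible text of SAP Section 10 does not list it as a change, though part of that section cannot be seen.

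**Step 3: whether such a record can exist.** Two routes remain.

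- *Week-36 rollovers* under observation before an OLS dose. Protocol 8.3.1 does not say whether study drug, or exposure to treatment, means the OLS injection alone. Its medical-history rule begins "A pre-existing condition is one that is present prior to the start of the study", so it does not cover a new event arising between OLS entry and the first OLS injection.
- *Missing causality.* A blank rating is counted as definite. The SAP does not limit this to AEs that have already met the onset rule, so a pre-dose AE with a blank rating could become both related and treatment-emergent. This route is not confined to rollovers.

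**Step 4: size per subject.** Let k be the number of subjects in a table cell whose only related treatment-emergent AE is a pre-dose event, and n the denominator. Added incidence in percentage points = 100 × k / n. For n, use the exposure counts in SAP 3.6 and Protocol 9.1: about 350 treated once, at least 100 with 3 or 4 cycles, and at least 50 with 3 or 4 high-dose cycles. The values of k are assumed.

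| k (assumed) | n = 350 | n = 100 | n = 50 |
|---|---|---|---|
| 0 | 0 | 0 | 0 |
| 1 | 0.29 | 1 | 2 |
| 2 | 0.57 | 2 | 4 |
| 5 | 1.43 | 5 | 10 |
| 10 | 2.86 | 10 | 20 |

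For example, 100 × 1 / 350 = 0.29 and 100 × 1 / 50 = 2. An affected subject who also has a genuine post-dose related AE in the same cell is counted anyway and adds nothing. The per-subject figures are therefore upper limits.

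**The case against.** The strongest reply is that the protocol leaves the sentence almost nothing to act on. An AE must emerge or worsen after study drug (8.3.1). Significant examination findings before dosing go to Medical History (8.2.1, 8.2.2). AEs are assessed after treatment and at later visits (8.3.5). Dysphagia counts only if it is found after baseline and is new or worse than at baseline (8.2.10). SAP 6.2 sets Day 1 as the day study medication is first given, which suggests that the term means OLS drug; a reaction to the parent-trial injection would then not be related to it. Some rollovers had placebo. A Week-36 rollover never dosed in the OLS is outside the safety population (SAP 5.3). Finally, the AE listing shows onset relative to first dose, so any such event can be seen.

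Most of this stands, and it is why the number may be zero. It does not rescue the sentence. If the protocol rules work perfectly, the sentence is redundant; if they do not, it counts the wrong events. If it was meant for incomplete start dates, it does not say so. A listing lets a reader spot the problem but does not correct the table.

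Three stronger readings are tempting, and the documents do not support them.

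- *Pre-dose events will fall into Cycle 1 at the dose given later.* No rule assigning AEs to a cycle is visible, and nearby SAP text is redacted, so the allocation cannot be stated as fact.
- *The rule biases a comparison of rollover with de novo subjects.* SAP 7.1 splits enrollment that way, but the visible AE tables are by dose, cycle and dose-frequency group.
- *The drug-related rate is inflated by some stated percentage.* The documents give neither a rate of pre-dose related AEs nor a true Cycle 1 rate.

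**Conclusion.** The point holds as a definitional error of unknown and possibly nil effect. The relatedness sentence conflicts with the protocol's definitions. With dates known, it can change the analysis only by admitting events that belong to no OLS dose or cycle. Such events can enter the treatment-related tables behind a primary endpoint; nothing shows that they will.

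The cost is at most 0.29 percentage points per affected subject on about 350, and at most 2 points on the minimum high-dose group of 50. These figures assume that the regulatory exposure counts serve as denominators. A single-dose cell within a cycle could have a different denominator, which the visible text does not give. The conclusion also assumes that no redacted passage already restricts the sentence by onset.

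**What to change.** - Delete the relatedness sentence from SAP 9.3, or limit it to AEs with onset or worsening on or after the first OLS injection.
- Apply the missing-causality rule only to AEs that already meet the onset rule.
- In the existing AE listing, flag related AEs that began before the first OLS injection, so that possible carry-over from Study 1720302 stays visible without entering the incidence.

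The cost is one sentence deleted or amended, one qualifying clause and one flag in a listing already planned. No safety information is lost, because SAP 9.3 lists all AEs in any case.

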After a subject has decided to enroll in the OLS, s/he will have up to 21 days to complete the screening procedures and enroll in the OLS. After 21 days, subjects who have NOT completed the screening procedures will be considered a screen failure. To be reconsidered for enrollment to the OLS, the subject will be required to repeat all screening procedures to reconfirm eligibility for enrollment in the OLS. These criteria also apply to subjects who missed the 7-day decision-making window to enroll in the OLS.

A written informed consent must be obtained from all subjects participating in the OLS before any trial-related procedures (including any screening procedures) are performed.

Eligible subjects who completed participation in Study Protocol 1720302 may be eligible for the first treatment (Baseline Treatment in Treatment Cycle 1 of OLS) during their EOS Visit window, but treatment may not be administered on the same day as the EOS Visit due to unavailability of screening safety laboratory results. In this case, the EOS Visit procedures and laboratory results from Study Protocol 1720302 will serve as the baseline data for this trial.

This study will also recruit new BoNT treatment-naïve or -experienced adult subjects, who were not enrolled in Study Protocol 1720302.

[REDACTED]

[REDACTED]

[REDACTED]

- [REDACTED]

- [REDACTED]

[REDACTED]

- [REDACTED]

- [REDACTED]

[REDACTED]

[REDACTED]

[REDACTED]

[REDACTED]

Two weeks after the Baseline/Treatment Study Visit (Day 1), study site staff will call the subject to inquire about CD symptom status and adverse events (AEs). The subject will return for protocol-specified assessments at Weeks 4, 6, 12, and every 4 weeks thereafter, up to Week 52 or EOS Visit.

Primary endpoints are safety and immunogenicity after multiple continuous treatment cycles of DAXI for injection. [REDACTED]

[REDACTED]

[REDACTED]

[REDACTED]

[REDACTED]

[REDACTED]

[REDACTED]

A subject may not be re-enrolled in the OLS after the EOS Visit (or after early discontinuation).

Study Visits and Telephone Calls:

- Screening (Days -21 to -1)
- Treatment #1, #2, #3, and #4
- Follow-up telephone calls after each Treatment:
 - Week 2 after each treatment (study site staff will call the subject)
- Follow-up visits after each Treatment:
 - Follow-up visits at Weeks 4, 6, 12, and every 4 weeks thereafter until the EOS Visit (52 weeks after Treatment #1 [Study Baseline]) (See Figure 1 Figure 1 and Table 1).

Safety Evaluations:

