5 STUDY POPULATION

5.1 INCLUSION CRITERIA

All participants must meet the following inclusion criteria:

1. Adults, 18 to 80 years of age

[figure not shown]
2. Meets diagnostic criteria for isolated CD (idiopathic; dystonic symptoms localized to the head, neck, shoulder areas) with at least moderate severity at Baseline (Day 1), defined as a TWSTRS-total score of at least 20, with at least 15 on the TWSTRS-Severity subscale, at least 3 on the TWSTRS-Disability subscale, and at least 1 on the TWSTRS-Pain subscale (minimum TWSTRS subscale criteria applicable only to subjects not previously enrolled in Study Protocol 1720302)
3. Subjects who were previously enrolled in Study Protocol 1720302, who completed the study, including:
 - a) Those with no reduction or have an increase from baseline in the average TWSTRS-total score at Weeks 4 and 6 (i.e., no improvement or worsened disease status), and the investigator agreed that there was a need for retreatment based on the subject's symptoms and neurologic examination findings
 - b) Those who benefited from study treatment and complete follow-up study visits up to the time point of when their TWSTRS-total score reached/exceeded their target TWSTRS score
 - c) Those who benefit from study treatment but subsequently experienced significant recurrence of CD symptoms (e.g., pain) during the study before their TWSTRS-total score reached their target TWSTRS score and requested retreatment, which the investigator determined was warranted due based on the subject's symptoms and neurologic examination findings
 - d) Those who completed study visits up to Week 36 and their TWSTRS-total score never reached their target TWSTRS score and they never requested another treatment. The investigator determined that these subjects can be followed in the OLS until their TWSTRS-total score is the same or higher than their target TWSTRS score or until they request retreatment, which the investigator determined is clinically indicated
4. De novo subjects (not previously enrolled in Study Protocol 1720302):
 - a) Naïve to BoNT treatment
 - b) BoNT treatment-experienced; if previously treated with BoNTA, the subject must have demonstrated a clinically meaningful response to the last BoNTA treatment based on the clinical judgment of the investigator
5. Written informed consent including authorization to release health information

[figure not shown]

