3.4. Brief Description

This is a Phase 3, open-label, multi-center trial to evaluate the long-term safety, efficacy, and immunogenicity of up to four continuous treatment cycles of DAXI for injection at doses of 125 U, 200 U, 250 U, and 300 U in adults with isolated CD at study centers across the United States, Canada, and Europe.

Approximately 350 adult subjects will be recruited from study centers who were previously enrolled in Protocol 1720302 entitled [A Phase 3, Randomized, Double-Blind, Placebo-Controlled, Parallel Group, Multi-Center Trial to Evaluate the Efficacy and Safety of a Single Treatment of DaxibotulinumtoxinA for Injection in Adults with Isolated Cervical Dystonia (ASPEN-1)]. These subjects will have 7 days from their End-of-Study (EOS) Visit in Protocol 1720302 to decide if they want to enroll in this study. After enrolling, subjects will have up to 21 days to complete screening procedures. After 21 days, subjects who have NOT completed the screening procedures will be considered a screen failure. To be reconsidered for enrollment to this study, the subject will be required to repeat all screening procedures to reconfirm eligibility for enrollment. These criteria also apply to subjects who missed the 7-day decision-making window to enroll in this study. This study will also recruit new botulinum neurotoxin (BoNT) treatment-naïve or -experienced adult subjects who were not enrolled in Protocol 1720302.

[REDACTED]

[REDACTED]

This document is confidential.

[REDACTED]

The primary endpoints are safety and immunogenicity. [REDACTED]

[REDACTED]

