7.1. Subject Disposition and Withdrawals

The number and percentage of subjects screened, enrolled, completed, and discontinued will be summarized along with the reasons for discontinuation and will be summarized. The number of subjects who received treatment in each cycle will be summarized. The number of subjects in each study analysis population will also be presented. Enrollment will be summarized by Rollover and DeNovo. Listings will be provided for disposition data, study populations and reasons for exclusion from the study population, and inclusion/exclusion criteria not met.

The reason for discontinuation will also be summarized by cycle. A summary of the duration of the subject participation in the study will be produced, including the n, mean, SD, median, minimum, and maximum duration in weeks, as well as the number and percentage of subjects in the following categories of duration: <4 weeks, 4 to <12 weeks, 12 to <24 weeks, and 24 to <36 weeks, and 36 weeks or more. If a subject is lost to follow-up, their participation in the study will be calculated based on their date of last visit. Duration of study participation will also be summarized overall, across all cycles using the following categories: < 24 weeks, 24 to < 36 weeks, 36 to < 48 weeks, and 48 weeks or more.

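### Cycle numbers restart in the open-label study, so cycle-1 AE incidence pools first and second DAXI exposures, and no visible table separates them

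*SAP*

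**What the plan says.** SAP 4.1 makes the incidence of drug-related AEs, of stopping study drug because of them, and of treatment-emergent immunogenicity primary, each by dose and by cycle. SAP 9.3 sets the layout of the AE tables: "Summary tables will be provided for treatment-emergent AEs (TEAEs) by dose and treatment cycle and overall for the following".

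The Protocol synopsis treats a rollover subject's first OLS injection as the start of cycle 1 ("first treatment (Baseline Treatment in Treatment Cycle 1 of OLS"). SAP 3.4 gives the main source of subjects: "Approximately 350 adult subjects will be recruited from study centers who were previously enrolled in Protocol 1720302". It describes that parent study as "Placebo-Controlled, Parallel Group, Multi-Center Trial to Evaluate the Efficacy and Safety of a Single Treatment of DaxibotulinumtoxinA". De novo subjects, either naive to botulinum toxin or experienced with it, are also recruited; their number is not in the visible text.

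Protocol 5.1, criterion 3, admits "Subjects who were previously enrolled in Study Protocol 1720302, who completed the study, including" four categories, among them non-responders and subjects who asked for early retreatment.

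The visible SAP separates the two sources of subjects in one place, section 7.1: "Enrollment will be summarized by Rollover and DeNovo". SAP 9.3 also forms four groups by dose level (low or high) and number of cycles (1 or 2, against 3 or 4). It does not mention an injection received in 1720302.

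**The concern.** A rate by cycle helps answer a question about repeated treatment if the cycle number tracks how often subjects have been exposed. Here each cycle number covers two exposure histories. A subject given DAXI in 1720302 is one injection ahead of a placebo rollover or a de novo subject in the same cycle.

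The groups also enter by different routes. Every rollover had to complete 1720302. For those given DAXI, this may also select on having stayed in follow-up after an earlier DAXI injection. De novo subjects face no such requirement.

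At stake is how the primary tables are read. If AE incidence is flat, rising or falling across cycles, the pooled table cannot show whether risk changes with repeated treatment or whether the mix of exposure histories differs between cycles.

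**Working it through.** **Exposure by cycle.** The plan's own ceiling is up to four cycles. Protocol 8.1.3 rules out retreatment within 12 weeks of the last injection or after Week 40. Injections at Weeks 0, 12, 24 and 36 give 4, which agrees. Cumulative DAXI injections are then the OLS cycles for placebo rollovers and de novo subjects (as far as the visible text shows), and the OLS cycles + 1 for DAXI rollovers:

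| OLS cycles received | Placebo rollover or de novo | DAXI rollover | SAP 9.3 group by OLS cycles | Group if the parent injection counted |
|---|---|---|---|---|
| 1 | 1 | 2 | low frequency | low |
| 2 | 2 | 3 | low frequency | high |
| 3 | 3 | 4 | high frequency | high |
| 4 | 4 | 5 | high frequency | beyond the 3-or-4 range |

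Only DAXI rollovers with exactly 2 OLS cycles would move from low to high.

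**How many subjects.** The parent allocation is not in the documents. If 50%, 67% or 75% of 350 rollovers had received DAXI (assumed), cycle 1 would be a second exposure for 175, about 233 or about 262 of them. As a share of all cycle-1 subjects this also depends on the de novo number. With 200 de novo subjects (assumed) and two-thirds of rollovers on DAXI, the share is 233/(350 + 200) = 42%. A range of 25% to 75% is used below.

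**Effect on the cycle-1 rate.** Let f be the share of cycle-1 subjects with prior DAXI, p1 the incidence at first exposure and p2 the incidence at second exposure. The pooled rate is (1 − f) × p1 + f × p2. The documents give no AE rates, so every p is an assumption:

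| p1 | p2 | f = 25% | f = 50% | f = 67% | f = 75% |
|---|---|---|---|---|---|
| 20% | 20% | 20.0% | 20.0% | 20.0% | 20.0% |
| 20% | 15% | 18.8% | 17.5% | 16.7% | 16.2% |
| 20% | 10% | 17.5% | 15.0% | 13.3% | 12.5% |

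For example, 0.5 × 20% + 0.5 × 10% = 15.0%. If risk rises with exposure the sign reverses: p1 = 10% and p2 = 20% at f = 50% also give 15.0%, now above the first-exposure rate.

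**Effect on the pattern across cycles.** Suppose the rates stayed at 20% in subjects without prior DAXI and 10% in those with it, in every cycle (assumed). If the prior-DAXI share among those still being treated went from 50% to 67%, the pooled rate would fall from 15.0% to 13.3% with no change in either group.

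**Exposure targets.** SAP 3.6 asks for at least 100 subjects with three or four consecutive cycles, at least 50 of them at high dose. Counting OLS cycles alone leaves some subjects with three DAXI treatments in the low-frequency groups. It adds nobody to the high-frequency groups, so it cannot inflate either count.

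**The case against.** The strongest reply is that the plan follows its own definitions. The study is described as up to four consecutive cycles, cycle 1 is the first OLS treatment, and the exposure target uses the same unit. A reader might infer that the frequency groups miscount consecutive treatments. The documents do not support that, because nothing visible places the parent injection in the series. What can be said is that cumulative exposure is undercounted for DAXI rollovers.

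A reader might also infer that cycle 1 understates first-exposure risk by some stated amount. That would need AE rates, the parent allocation and the de novo number, and the visible text gives none of them. Nor does it present cycle 1 as an estimate of first-exposure risk: the parent trial studied a single treatment, and the AE tables here are descriptive.

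Third, one might read the completion requirement as removing AE dropouts from the prior-DAXI subjects alone. It applies to placebo rollovers too. Non-responders and early retreatment requests still qualify. The parent trial had no repeat dosing to stop, only follow-up to leave. De novo subjects previously treated with botulinum toxin type A carry a selection of their own, on response to their last such treatment. A strong tolerability filter is therefore not shown.

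Finally, text is redacted directly after the AE table list, between SAP 9.3 and 9.5, and between SAP 6.2 and 6.4. A split by prior exposure may be there, so its absence can be asserted for the visible text only.

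All of this limits the claim. It does not remove the mixing of exposure histories within each cycle, and the parent injection is not foreign to the plan: Protocol 9.6 measures duration of effect from the 1720302 injection date for certain Week 36 rollovers.

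**Conclusion.** The point holds in a limited form. In the visible plan, cycle-1 incidence of drug-related AEs combines first and second DAXI exposures, cycle 4 can be a fifth injection, and no visible AE table separates these histories. The size and direction of any effect are unknown; it is zero if rates do not depend on prior exposure. The tabulated rates show only what pooling would do under assumed inputs.

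The frequency groups are consistent with the study's definition of a cycle, but class a DAXI rollover with three DAXI treatments as low frequency when two of them were in the OLS. The 100 and 50 targets are not affected in the sponsor's favour.

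This is a cheap improvement to the reading of a primary endpoint. It rests on two readings of the visible text: that cycle numbering restarts for all rollovers, and that no redacted section already provides the split.

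**What to change.** Keep the pooled tables in SAP 9.3 and add:

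1. Supplementary tables of the three primary endpoints (drug-related AEs, discontinuation of study drug due to drug-related AEs, treatment-emergent immunogenicity) by cycle for three groups: 1720302 DAXI rollovers, 1720302 placebo rollovers and de novo subjects. Placebo rollovers and de novo subjects should stay apart because only the former had to complete the parent trial.
2. One AE table by cumulative DAXI injection number, 1 to 5.
3. A sentence stating that the frequency groups count OLS cycles only.

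If a redacted section already contains these, confirm it and change nothing.

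The cost is SAP wording, one merge of the 1720302 treatment code and a few extra tables. The tables are descriptive, so no alpha or power is spent. The drawback is small cells: 4 doses × 4 cycles × 3 groups = 48. Collapsing dose to low and high where cells are small gives 2 × 4 × 3 = 24.
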